
- **Session 1:** CBT Model & Goal Setting
 - Pain integrated into CBT model; goals also associated with addressing pain-related functional impairment
- **Session 2:** Identifying & Challenging Thoughts I
 - Pain-related thoughts perpetuating loneliness; loneliness-related thoughts perpetuating pain
- **Session 3:** Identifying & Challenging Thoughts II
 - Continued focus pain-related thoughts perpetuating loneliness; loneliness-related thoughts perpetuating pain
- **Session 4:** Assertiveness Training
 - Teaching effective communication and conflict resolution

- Session 5: Exposure & Behavioral Activation I
 - Incorporating physical activity into exposure and behavioral activation related to social activities
- Session 6: Exposure & Behavioral Activation II
 - Incorporating physical activity into exposure and behavioral activation related to social activities
- Session 7: Problem Solving
 - Problem solving issues around functional limitations, mobility, and other pain-related barriers
- Session 8: Review & Relapse Prevention
 - Review is specific to new content, using skills for CBT-L to address pain flares

CBT-CP: A Cochrane review indicated that CBT-CP reduces pain intensity, disability, mood outcomes, and pain catastrophizing.³³ CBT-CP is a nationally disseminated, evidence-based intervention with the goal of increasing functioning and quality of life through adaptive pain coping skills to support self-efficacy to manage pain.³⁴⁻³⁶ This is accomplished through pain psychoeducation, increasing activity level (e.g., walking, pleasant activities), and identifying and challenging pain catastrophizing. This CBT-CP protocol will be reduced from 10 to 8 sessions to match the number of sessions to CBT-L. The sleep hygiene session will be removed, and goal setting will occur in session 1 (rather than a stand-alone session). Both changes are consistent with Brief CBT-CP that was created in the VHA.³⁷ The manual is included as an **Appendix**.

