5.6 Schedule of Assessments

Schedule of Assessments – One Arm Trial			
Measures	Screening	Baseline	Post-treatment
Eligibility Review	X		
NIH Toolbox Loneliness Scale	X		
PEG	X		
Demographics and Military Background		X	
Brief Pain Inventory		X	X
Revised UCLA Loneliness Scale		X	X
Duke Social Support Index (DSSI)		X	X
Treatment Services Review (TSR)		X	X
PROMIS-29 (less pain subscale)		X	X
Interpersonal Needs Questionnaire-12		X	X
Pain Catastrophizing Scale (PCS)		X	X
Tampa Scale of Kinesiophobia		X	X
Pain-related Self-Efficacy Questionnaire (PSEQ)		X	X
Paykel Suicide Scale		X	X
Current Opioid Misuse Measure (COMM)		X	X
Exit Interview/Abbreviated Acceptability Rating Profile (AARP)			X

Schedule of Assessments –Randomized Clinical Trial

Measures	Screening	Baseline	Post-treatment	1-mo follow-up
Eligibility Review	X			
NIH Toolbox Loneliness Scale	X			
PEG	X			
Demographics and Military Background		X	X	
Brief Pain Inventory		X	X	X
Revised UCLA Loneliness Scale		X	X	X
Duke Social Support Index (DSSI)		X	X	X
Treatment Services Review (TSR)		X	X	X
PROMIS-29 (less pain subscale)		X	X	X
Interpersonal Needs Questionnaire-12		X	X	X
Pain Catastrophizing Scale (PCS)		X	X	X
Tampa Scale of Kinesiophobia		X	X	X
Pain-related Self-Efficacy Questionnaire (PSEQ)		X	X	X
Paykel Suicide Scale		X	X	X
Current Opioid Misuse Measure (COMM)		X	X	X
Exit Interview			X	

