6.0 Protection of Human Subjects

Risk to Participants

Human Subjects Involvement and Characteristics. The purpose of this study is to assess the feasibility and acceptability of an intervention designed to improve social functioning and pain interference in functioning among Veterans with chronic pain. A total of 48 participants (n = 8 for the Aim 1 one-arm trial and n = 40 for the Aim 2 RCT) will be recruited across the US. According to national survey data, 65.5% of Veterans reported experiencing pain in the last 3 months. While Veterans reporting pain tended to be older (60+ years = 56.5%), 12% were comprised of 18-39 year olds, 13.4% were comprised of 40-49 year olds, and 17.9% were comprised of 50-59 year olds. 92.5% were men, while just 7.5% were women, however, women were slightly more likely to report pain in the last 3 months compared to men (70.1% vs. 65.3%). VHA data indicate that medical and psychiatric comorbidity is high among Veterans with musculoskeletal conditions (many of which are associated with chronic pain). We expect that the recruitment pool will be similar to the above estimates; however, we will use recruitment ads to promote recruitment of women and Veterans with minority status to increase representation in our sample.

Source of Materials. Study materials will include self-report questionnaires. The materials will be collected for study purposes only. Information collected will be stored in a locked filing cabinet in a locked office at the study sites that can only be accessed by members of the study team. *All electronic data* will be stored on VA Informatics and Computing Infrastructure (VINCI) project servers. Only approved study team personnel who will be involved in data entry, management and analyses will be granted access to this data. All computers are password protected.

Potential risks.

Psychological distress. Anticipated risks to the participants from assessment procedures and therapy are minimal; however, participants may experience psychological distress, frustration, and/or fatigue. The semi-structured interviews, assessments associated with the intervention, and therapy sessions may encourage participants to recall personal events and life stressors that may evoke distress. Additionally, confidentiality may need to be breached if a participant poses a threat to him or herself or others, including child abuse.

Adequacy of Protection from Risk

Recruitment and Informed Consent.

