All participants will be provided the VCL phone number at the end of each baseline assessment and at each follow-up assessment and encouraged to call the number should they become suicidal, simply wish to talk with someone, or would like assistance in obtaining a referral for mental health treatment. In situations in which potential suicide risk is identified during a phone call, we plan to use two levels of response: 1) researcher transfers the individual to the VCL (used in acute crises requiring emergency intervention or "rescue"); 2) researcher offers the participant a transfer to the VCL, but does not perform the transfer if he/she does not wish to be transferred (used in non-emergency situations).

Breach of Confidentiality. Statistical electronic data files will be kept VINCI project servers maintained by VINCI OI&T personnel and only summarized data without protected health information (PHI) will be downloaded from VINCI to local storage media. Research staff will use an audited VINCI download utility to move summarized data for reports, presentations and publications from VINCI servers to local storage media. The VINCI download utility provides an audit path including a copy of the downloaded material. The data extraction tool will be adapted for use with software directly available on the VINCI platform (e.g. Microsoft Word and Excel) and study data will be stored and maintained on VINCI. All study team personnel with access to sensitive patient data will stay current on their VA approved information security training and VA approved privacy policy training.

Adverse Events (AE). AEs may include, but are not limited to: worsened physical or mental health, or inadvertent disclosure of confidential research information. Serious Adverse Events (SAE) may include: death, hospitalization due to worsening psychiatric symptoms or suicidal ideation, or all life threatening or disabling/incapacitating events among research participants. Per IRB regulations, SAEs, any event resulting in a deviation from the study protocol (e.g., emergency hospitalization to address suicidal behaviors) or death will be reported to the PI within 24 hours and to the IRB in 48 hours. This will be completed in order to assess significance and determine an appropriate response. AEs that involve temporary distress will be noted by interviewers and provided to the IRB in an annual report.

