Data Safety. To ensure safety of participants in the study proposed and validity and integrity of data collected, the PI ([name]) will oversee all data and safety monitoring functions and the research team will be advised that he will be the primary contact overseeing these activities. The investigators will meet regularly to monitor study progress and discuss the implementation of monitoring procedures. The PI will also meet regularly with the research coordinator and staff to review monitoring procedures and ensure all efforts are being taken to minimize risks to participants. As indicated below, the PI will track all negative outcomes and incidents as well as conduct interim data analysis every 12 months after the study has started. The study design will be significantly modified (and even screening stopped) if the study is creating potential harm to our participants.

The PI and [name] will regularly oversee all aspects of the study, including participant recruitment, informed consent, data collection, management, and analysis, as well as regularly assess the risk/benefit ratio associated with participation in the study. All research staff will participate in an intensive training to help them understand the importance of reducing the risk for participants and learning how to recognize and report any AE or SAE. SAEs may include: death, hospitalization due to worsening psychiatric symptoms or suicidal ideation, or all life threatening or disabling/incapacitating events among research participants. AEs may include, but are not limited to: physical injuries, worsened physical or mental health, or inadvertent disclosure of confidential research information.

If an SAE occurs, the PI will immediately contact the IRB, followed by a written report in 24 hours. He will make a decision whether there is sufficient evidence to suspend data collection, allow for further IRB review, modify the protocol, or make other changes to reduce potential risk to participants. The study will resume based on agreement of the PI and IRB chair. In the event that an AE that is not an SAE is reported to the PI, the PI will discuss the event with the IRB chair. Immediate evaluation will occur to determine if any extra steps can be taken to minimize

the likelihood of that type of AE occurring again. If changes can be made, a report/amendment will be written and submitted to the IRB.

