As part of a standard practice, the PI will supervise the implementation of one audit regularly per year of the materials collected and produced as part of the study to ensure proper confidentiality and compliance with ethical principles, including informed consents, questionnaire data, and to make sure that the research staff are following established protocols. The PI will provide an annual summary report of all AEs to the IRB as part of the annual review. If no adverse events have occurred, the report will state, "No adverse events affecting human participants have occurred during this project year."

Data Monitoring. To ensure adequate participant recruitment and enrollment, each week, the PI will discuss the current number of participants contacted, screened, and enrolled from each site and compare those numbers to the expected based on our preliminary data. If after the first 4 months, it appears we are not reaching our expected number of participants, the PI will discuss potential barriers/obstacles and solutions. Discussions regarding recruitment and enrollment will continue at each meeting with study staff to ensure proper implementation of the study.

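### No scheduled assessment includes an adverse-event or injury query, and no rule turns worse scores or medical visits into adverse events, so physical harms that are not volunteered may go unrecorded

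*Combined protocol and SAP*

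**What the plan says.** **What counts as an AE.** Section 6.0 gives two lists. The Data Safety paragraph says "AEs may include, but are not limited to: physical injuries, worsened physical or mental health". The Adverse Events paragraph says "AEs may include, but are not limited to: worsened physical or mental health" and does not name injuries. The Potential risks paragraph covers psychological distress and breach of confidentiality only, and states "Anticipated risks to the participants from assessment procedures and therapy are minimal".

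**What the treatments ask of participants.** In section 5.1, sessions 5 and 6 of CBT-L/P are described as "Incorporating physical activity into exposure and behavioral activation related to social activities". CBT-CP works partly through "increasing activity level (e.g., walking, pleasant activities". Section 5.4 requires a score of at least 4 of 10 on each of the three PEG items, so everyone enrolled has appreciable pain.

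**How AEs reach the record.** One AE type has a named collector: "AEs that involve temporary distress will be noted by interviewers and provided to the IRB in an annual report". Other non-serious AEs enter the process once someone has reported them to the principal investigator. Staff are trained to identify and report AEs, and the principal investigator keeps track of negative outcomes. If no AE has occurred in a year, the annual report carries a set sentence: "No adverse events affecting human participants have occurred during this project year".

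**What is scheduled.** Neither the one-arm table in section 5.6 nor the table headed "Schedule of Assessments –Randomized Clinical Trial" has a row for AEs, injuries, falls or pain flares. Section 5.7 describes no summary of harms.

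**The concern.** The plan recognizes physical injury as a harm, and it gives treatments that raise activity in people with chronic pain. It does not say how anyone will find out that such a harm occurred. Suicidality is handled differently: it has a scheduled scale (the Paykel) and a detailed response pathway.

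Two things depend on ascertainment. One is the annual AE report to the IRB. The other is the commitment in the Data Safety paragraph to modify the design if the study may be harming participants. Without a question, a record of no physical events does not separate none having happened from none having been mentioned. The study is also meant to inform a larger trial, which would start with little usable information on physical harms.

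**Working it through.** **Step 1: could the scheduled measures stand in for an AE question?** Each is set against the role that sections 5.5 to 5.7 and 6.0 give it.

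| Source | When | What it picks up | What is missing |
|---|---|---|---|
| Brief Pain Inventory | Baseline, post-treatment, 1 month (RCT) | Pain severity and interference | No question on an event; no threshold for an AE |
| PROMIS-29 (less pain subscale) | Same | Physical function, fatigue | Same |
| Modified Treatment Services Review (TSR) | Same | Primary and specialty care visits | No rule that a visit is checked as a possible AE |
| Session-by-session feedback | During treatment | Reasons for drop-out and non-adherence | Harms not mentioned; form not shown |
| Exit interview | Post-treatment | Impressions and impact of treatment, therapist relationship, improvements | Harms not mentioned; guide not shown |
| Staff training | Before and during study | Recognizing and reporting AEs | No step that asks for them |
| Tracking by the principal investigator | Ongoing | Negative outcomes | Source of the information not given |

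Worsened physical health that persists to an assessment can show in the first three rows. A fall, a minor injury or a flare that settled beforehand and led to no medical visit need not show in any of them.

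**Step 2: illustration of size.** The documents give no event rate and no capture rate, so there is no figure to reproduce. Let *r* be the risk that a participant has a physical event, *c* the chance that the event is recorded, and *n* the number of participants. With participants independent:

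P(no event recorded) = (1 − r × c)^n

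Section 3.0 gives n = 20 per arm and 40 in the RCT. The values of *r* and *c* are assumptions.

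| r | c | n = 20 | n = 40 |
|---|---|---|---|
| 5% | 100% | 0.95^20 = 36% | 0.95^40 = 13% |
| 5% | 50% | 0.975^20 = 60% | 0.975^40 = 36% |
| 5% | 25% | 0.9875^20 = 78% | 0.9875^40 = 60% |
| 10% | 100% | 0.90^20 = 12% | 0.90^40 = 1.5% |
| 10% | 50% | 0.95^20 = 36% | 0.95^40 = 13% |
| 10% | 25% | 0.975^20 = 60% | 0.975^40 = 36% |
| 20% | 100% | 0.80^20 = 1% | 0.80^40 < 0.1% |
| 20% | 50% | 0.90^20 = 12% | 0.90^40 = 1.5% |
| 20% | 25% | 0.95^20 = 36% | 0.95^40 = 13% |

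**Step 3: what a zero count would support.** With full capture, the one-sided 95% upper bound after zero events is 1 − 0.05^(1/n). That is 13.9% for 0 of 20 and 7.2% for 0 of 40. If only a share *c* of events is recorded, the bound applies to r × c, so the bound on *r* is divided by *c*. At c = 50% it becomes 13.9% / 0.5 = 27.8% for an arm and 7.2% / 0.5 = 14.4% for the RCT.

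**The case against.** The strongest reply is that physical health is asked about. Both AE lists include worsened physical health, and pain, physical function, fatigue and medical visits are collected post-treatment, and again at 1 month in the RCT. Staff are trained on AEs, therapists see participants over eight sessions with weekly supervision, and the later CBT-L/P sessions discuss functional limitations and flares. People with recent or upcoming surgery or unstable medical conditions are excluded. All of this stands, and it limits the gap to discrete or transient events that leave no trace at an assessment and are not volunteered.

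A reader might infer three stronger things that the documents do not support:

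- **That physical harm is never asked about at any visit.** The Brief Pain Inventory, PROMIS and TSR items contradict this.
- **That a statement of no AEs would be issued by default.** The sentence is conditional on none having occurred, and it covers every AE type. A single note of distress would rule it out, so missed physical events alone do not produce it.
- **That comparisons between arms would be biased.** No between-arm AE comparison is planned; the analyses in section 5.7 are descriptive. Audio recording is stated for CBT-L/P sessions only, but its stated purpose is fidelity.

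There is also a limit to what can be checked. The manuals and interview guide are appendices that are not shown, nor is the feedback form. A prompt about physical harm may sit in one of them.

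**Conclusion.** The point holds in a limited form. The plan has no structured AE or injury query at any scheduled assessment and no rule that links a worse pain or function score, or a medical visit, to AE recording. Training and tracking supply no step that elicits events. A fall, injury or transient flare that is not volunteered may go unrecorded.

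The size cannot be estimated from the documents. At an assumed 10% risk, incomplete capture of 50% to 25% raises the chance of an empty physical-harm record from 12% to 36–60% in an arm of 20, and from about 1.5% to 13–36% across the RCT. These figures depend on the assumed risk and capture and on independence between participants. They concern physical events only, not the annual statement on all AEs.

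The AE and risk lists do not strictly conflict, since both AE lists are open-ended. They should still be aligned, because only one of the three paragraphs names physical injury. This is a cheap improvement to what the trial records, and it does not call the feasibility aims into question.

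**What to change.** 1. Add an 'Adverse events' row to both section 5.6 schedules: post-treatment in each, plus 1 month in the RCT. Ask one neutral open question, then a short prompt on injury, fall and urgent care, with the same wording in both arms. If an appendix already contains such a prompt, cite it in section 5.6 and confirm that it is used in both arms.
2. Have staff check TSR medical visits reported at follow-up for possible AEs, and say so in section 6.0.
3. Add to section 5.7 a descriptive count, by arm, of participants with at least one event.
4. Reconcile the Potential risks, Adverse Events and Data Safety paragraphs in section 6.0 so that they treat physical injury in the same way.

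The cost is about two minutes per assessment call, a script line and one table. The recorded AE count may be higher than under the present plan. No treatment content, eligibility rule or outcome measure changes.
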